5.4.3 Immune-related Adverse Events

Subjects who develop an adverse event thought to be immune-related should have additional testing to rule out other etiologic causes. If laboratory results or symptoms indicate a possible

irAEs, then additional testing should be performed to rule out other etiologic causes. If no other cause is found, then it is assumed to be immune-related.

5.4.3.1 Procedures and Supportive Care Guidelines for Subjects Exhibiting Immune-Related Adverse Events

The treatment guidelines outlined in this section are intended to guide the Investigator if the events are deemed related to epacadostat or pembrolizumab. The Study Medical Monitor is available to discuss procedures for treating subjects exhibiting irAEs.

Subjects should receive appropriate supportive care measures as deemed necessary by the treating Investigator. Suggested supportive care measures for the management of adverse events with potential immunologic etiology are outlined below. Note that several courses of steroid tapering may be necessary as symptoms may worsen when the steroid dose is decreased. For each disorder, attempts should be made to rule out other causes such as metastatic disease or bacterial or viral infection, which might require additional supportive care.

IV systemic antibiotic treatment in order to ensure clearance of CRS-207 should be administered prior to initiation of systemic steroids required to treat suspected irAEs. However systemic steroids can be administered at the same time as systemic antibiotics if necessary due to the subject's condition.

- **Pneumonitis:**

- For **Grade 2 events**, treat with systemic corticosteroids. When symptoms improve to Grade 1 or less, steroid taper should be started and continued over no less than 4 weeks.
- For **Grade 3 and Grade 4 events**, immediately treat with IV steroids. Administer additional anti-inflammatory measures, as needed.
- Add prophylactic antibiotics for opportunistic infections in the case of prolonged steroid administration.

- **Diarrhea/Colitis:**

Subjects should be carefully monitored for signs and symptoms of enterocolitis (such as diarrhea, abdominal pain, blood or mucus in stool, with or without fever) and of bowel perforation (such as peritoneal signs and ileus).

- All subjects who experience diarrhea/colitis should be advised to drink liberal quantities of clear fluids. If sufficient oral fluid intake is not feasible, fluid and electrolytes should be substituted via IV infusion. For Grade 2 or higher diarrhea, consider gastrointestinal consultation and endoscopy to confirm or rule out colitis.
- For **Grade 2 diarrhea/colitis** that persists >3 days, administer oral corticosteroids.
- For **Grade 3 or 4 diarrhea/colitis** that persists >1 week, treat with IV steroids followed by high dose oral steroids.
- When symptoms improve to Grade 1 or less, steroid taper should be started and continued over no less than 4 weeks.

- **Type 1 diabetes mellitus (T1DM) (if new onset, including diabetic ketoacidosis [DKA]) or \geq Grade 3 Hyperglycemia, if associated with ketosis (ketonuria) or metabolic acidosis (DKA):**
 - For **T1DM** or **Grade 3** and **Grade 4** Hyperglycemia:
 - Insulin replacement therapy is recommended for T1DM and for Grade 3 and Grade 4 hyperglycemia associated with metabolic acidosis or ketonuria.
 - Evaluate subjects with serum glucose and a metabolic panel, urine ketones, glycosylated hemoglobin, and C-peptide.
- **Hypophysitis:**
 - For **Grade 2** events, treat with corticosteroids. When symptoms improve to Grade 1 or less, steroid taper should be started and continued over no less than 4 weeks. Replacement of appropriate hormones may be required as the steroid dose is tapered.
 - For **Grade 3** and **Grade 4** events, treat with an initial dose of IV corticosteroids followed by oral corticosteroids. When symptoms improve to Grade 1 or less, steroid taper should be started and continued over no less than 4 weeks. Replacement of appropriate hormones may be required as the steroid dose is tapered.
- **Hyperthyroidism or Hypothyroidism:**

Thyroid disorders can occur at any time during treatment. Monitor subjects for changes in thyroid function (at the start of treatment, periodically during treatment, and as indicated based on clinical evaluation) and for clinical signs and symptoms of thyroid disorders.

 - **Grade 2** hyperthyroidism events (and **Grade 2** to **Grade 4** hypothyroidism):
 - In hyperthyroidism, non-selective beta-blockers (e.g. propranolol) are suggested as initial therapy.
 - In hypothyroidism, thyroid hormone replacement therapy, with levothyroxine or liothyronine, is indicated per standard of care.
 - **Grade 3** and **Grade 4** hyperthyroidism:
 - Treat with an initial dose of IV corticosteroid followed by oral corticosteroids. When symptoms improve to Grade 1 or less, steroid taper should be started and continued over no less than 4 weeks. Replacement of appropriate hormones may be required as the steroid dose is tapered.
- **Hepatic:**
 - For **Grade 2** events, monitor LFTs more frequently until returned to baseline values (consider weekly or twice weekly if steroids are not initiated).
 - Treat with IV or oral corticosteroids.
 - For **Grade 3** and **Grade 4** events, treat with IV corticosteroids for 24 to 48 hours.
 - When symptoms improve to Grade 1 or less, a steroid taper should be started and continued over no less than 4 weeks.

- **Renal Failure or Nephritis:**

- For **Grade 2** events, treat with corticosteroids.
- For **Grade 3** and **Grade 4** events, treat with systemic corticosteroids.
- When symptoms improve to Grade 1 or less, steroid taper should be started and continued over no less than 4 weeks.

5.4.3.2 Procedures for other Severe Immune-Mediated Adverse Reactions, Including Ocular Manifestations

All study drugs should be permanently discontinued for severe (Grade 4) irAEs. Systemic corticosteroid treatment should be initiated at a dose of 1 to 2 mg/kg per day of prednisone or equivalent for severe irAEs.

Corticosteroid eye drops should be administered to subjects who develop uveitis, iritis, or episcleritis. Epacadostat should be permanently discontinued for immune-mediated ocular disease that is unresponsive to local immunosuppressive therapy.

5.4.3.3 Discontinuation Rules and Procedures for Immune-Related Adverse Events

Adverse events of a potential immunologic etiology or irAEs may be defined as an adverse event of unknown etiology, associated with drug exposure and consistent with an immune phenomenon. IrAEs may be predicted based on the nature of the compounds, their mechanism of action, and reported experience with immunotherapies that have a similar mechanism of action. Special attention should be paid to adverse events that may be suggestive of potential irAEs. An irAE can occur shortly after the first dose or several months after the last dose of treatment.

If an irAE is suspected, efforts should be made to rule out neoplastic, infectious, metabolic, toxin, or other etiologic causes prior to labeling an adverse event as an irAE. If other causes exist, additional supportive care may be required. Subjects who develop a \geq Grade 2 irAE should be discussed immediately with the Sponsor.

General supportive care recommendations to manage irAEs due to epacadostat are detailed in [Table 8](#). In addition, recommendations for prophylactic and supportive care measures of specific irAEs, infusion reactions, pneumonitis, hepatitis, dermatitis, immune-mediated neuropathies, immune-mediated endocrinopathies, and ocular manifestations are detailed throughout [Section 5.4](#).

irAEs may be attributable to one or more study drugs. If the event is clearly related to one of the agents, follow the instructions specific for that agent, if available. If the event is related to multiple agents, follow the action taken instructions provided, or consult the Study Medical Monitor.

Table 8 General Guidelines for Immune-Related Adverse Events Due to Epacadostat

irAE Toxicity Grade	Withhold/Discontinue Epacadostat*	Action Taken With Respect to Epacadostat	Supportive Care
Grade 1	No action.	Not applicable.	Provide symptomatic treatment.
Grade 2	May withhold epacadostat per Investigator's discretion.	May return to treatment if improves to Grade 1 or resolves within 6 weeks. If adverse event resolves within 4 weeks, subject may restart at the same dose and schedule for epacadostat. For an adverse event that does not resolve within 4 weeks, epacadostat should be reduced 1 dose level. If adverse event does not resolve within 6 weeks, study treatment with epacadostat should be discontinued or discussed with Study Medical Monitor.	Consider systemic corticosteroids in addition to appropriate symptomatic treatment.
Grade 3	Withhold or discontinue epacadostat. Discontinue if unable to reduce corticosteroid dose to <10 mg/day of prednisone or equivalent within 6 weeks of toxicity.	Any restart of study treatment must be discussed with Study Medical Monitor prior to restarting treatment.	Systemic corticosteroids are indicated in addition to appropriate symptomatic treatment. May use 1 to 2 mg/kg prednisone or equivalent per day. Steroid taper should be considered once symptoms improve to ≤ Grade 1 and tapered over at least 4 weeks in most cases.
Grade 4	Discontinue epacadostat.	Not applicable. Any exceptions require Study Medical Monitor approval.	Systemic corticosteroids are indicated in addition to appropriate symptomatic treatment. May use 1 to 2 mg/kg prednisone or equivalent per day. Steroid taper should be considered once symptoms improve to ≤ Grade 1 and tapered over at least 4 weeks in most cases.
irAE = immune-related adverse event. *in any of the above scenarios where epacadostat is held or discontinued, contact the Study Medical Monitor for guidance on continuation of CRS-207 treatment.			

Note that several courses of steroid tapering may be necessary as symptoms may worsen when the steroid dose is decreased.

It may be necessary to perform conditional procedures such as bronchoscopy, endoscopy, or skin photography as part of evaluation of the event.

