5.4.2 Criteria and Procedures for Dose Modification

CRS-207 has been well tolerated to date. The major safety signals have been infusion related reactions ([Section 5.5.2.1](#)). If a dose reduction of CRS-207 is being considered then the Study Medical Monitor should be contacted for further discussion.

Epacadostat dose may be reduced according to the guidelines and dose levels described in [Table 6](#). Additional information related to dose changes for epacadostat for specific adverse events can be found in [Section 5.4.3.3](#) for immune-related Adverse Events (irAEs) and [Section 5.4.6](#) for an adverse event of SS. Dose modifications for pembrolizumab-related events are provided in [Table 7](#).

If the subject experiences a new TEAE or is recovering from a TEAE, CRS-207 administration may be delayed up to 7 days following pembrolizumab administration; the Sponsor must be notified. If a dose of CRS-207 is delayed beyond 7 days of pembrolizumab, the dose of CRS-207 should be withheld until the next cycle.

Table 6 Dose Modification Guidance for Epacadostat

Toxicity	Hold Treatment For Grade	Timing for Restarting Treatment	Dose Level for Restarting Treatment	Treatment Discontinuation
Diarrhea/Colitis	2-3	Toxicity resolves to Grade 0-1	Related: Reduce by 1 dose level Not Related: Same dose level	Toxicity does not resolve within 12 weeks of last dose or inability to reduce corticosteroid to 10 mg or less of prednisone or equivalent per day within 12 weeks
	4	Permanently discontinue	n/a	Permanently discontinue
AST, ALT, or Increased Bilirubin ¹	2	Toxicity resolves to Grade 0-1	Related: Reduce by 1 dose level Not Related: Same dose level	Toxicity does not resolve within 12 weeks of last dose
	3-4	Permanently discontinue (see exception below) ²	n/a	Permanently discontinue
Type 1 diabetes mellitus (if new onset)	T1DM	Hold epacadostat for new onset Type 1 diabetes mellitus. Resume epacadostat when subjects are clinically and metabolically stable.	Related: Reduce by 1 dose level Not Related: Same dose level	Resume epacadostat when subjects are clinically and metabolically stable
Hyperglycemia	3-4	Hold epacadostat for Grade 3-4 hyperglycemia associated with evidence of beta cell failure. Resume epacadostat when subjects are clinically and metabolically stable.	Related: Reduce by 1 dose level Not Related: Same dose level	Resume epacadostat when subjects are clinically and metabolically stable

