Hypophysitis	2-4	Therapy with epacadostat can be continued while endocrine replacement therapy is instituted.	Related: Reduce by 1 dose level Not Related: Same dose level	Toxicity does not resolve within 12 weeks of last dose or inability to reduce corticosteroid to 10 mg or less of prednisone or equivalent per day within 12 weeks
Hyperthyroidism	3	Toxicity resolves to Grade 0-1	Related: Reduce by 1 dose level Not Related: Same dose level	Toxicity does not resolve within 12 weeks of last dose or inability to reduce corticosteroid to 10 mg or less of prednisone or equivalent per day within 12 weeks
	4	Permanently discontinue	n/a	Permanently discontinue
Hypothyroidism	1-4	Therapy with epacadostat can be continued while thyroid replacement therapy is instituted	n/a	Therapy with epacadostat can be continued while thyroid replacement therapy is instituted
Pneumonitis	2	Toxicity resolves to Grade 0-1	Related: Reduce by 1 dose level	

¹ Subjects with bone metastasis related elevations at baseline, contact sponsor to discuss clinical management and possible dose reductions of epacadostat.

² For subjects with liver metastasis who begin treatment with Grade 2 AST or ALT, if AST or ALT increases by greater than or equal to 50% relative to baseline and lasts for at least 1 week then subjects should be discontinued. For subjects have transient Grade 3 AST/ALT levels persisting for < 7 days and do NOT require steroids, epacadostat may reduce by 1 dose level once AST/ALT returns to baseline.

Toxicity	Hold Treatment For Grade	Timing for Restarting Treatment	Dose Level for Restarting Treatment	Treatment Discontinuation
			Not Related: Same dose level	Toxicity does not resolve within 12 weeks of last dose or inability to reduce corticosteroid to 10 mg or less of prednisone or equivalent per day within 12 weeks
	3-4	Permanently discontinue	n/a	Permanently discontinue
Renal Failure or Nephritis	2	Toxicity resolves to Grade 0-1	Related: Reduce by 1 dose level Not Related: Same dose level	Toxicity does not resolve within 12 weeks of last dose or inability to reduce corticosteroid to 10 mg or less of prednisone or equivalent per day within 12 weeks
	3-4	Permanently discontinue	n/a	Permanently discontinue

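### Protocol Tables 6 and 8 and Section 5.4.3.2 give inconsistent epacadostat rules for the same immune-related event, and nothing says which governs

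*Protocol*

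**What the plan says.** Protocol Section 5.4.2 makes Table 6 the guide for epacadostat reductions and then refers the reader to Section 5.4.3.3, which contains Table 8, for dose changes after immune-related adverse events (irAEs). Neither section says which prevails. The only tie-break, in Section 5.4.3.3, is by agent: if one drug is clearly responsible, follow that drug's instructions. Both tables are epacadostat instructions, so this does not choose between them.

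- **Table 6, named toxicities.** The restart cell for held events reads "Related: Reduce by 1 dose level Not Related: Same dose level". Where a steroid limit is given, treatment stops on "inability to reduce corticosteroid to 10 mg or less of prednisone or equivalent per day within 12 weeks"; non-resolution is also given 12 weeks. For Grade 2-4 hypophysitis: "Therapy with epacadostat can be continued while endocrine replacement therapy is instituted".
- **Table 8, Grade 2 irAE due to epacadostat.** "May withhold epacadostat per Investigator's discretion". On restart: "If adverse event resolves within 4 weeks, subject may restart at the same dose and schedule for epacadostat". On non-resolution: "If adverse event does not resolve within 6 weeks, study treatment with epacadostat should be discontinued or discussed with Study Medical Monitor".
- **Table 8, Grade 3.** Withhold or discontinue, with any restart discussed with the Medical Monitor first. "Discontinue if unable to reduce corticosteroid dose to <10 mg/day of prednisone or equivalent within 6 weeks of toxicity".
- **Section 5.4.3.2.** "All study drugs should be permanently discontinued for severe (Grade 4) irAEs". Table 8 at Grade 4 also discontinues epacadostat, unless the Medical Monitor approves an exception.

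**The concern.** The two tables cover the same events. Section 5.4.3.1 handles pneumonitis, diarrhea/colitis, new-onset type 1 diabetes or hyperglycemia, hypophysitis, thyroid, hepatic and renal events as irAEs, and each has its own row in Table 6. Table 8 is for irAEs due to epacadostat, so the branch of Table 6 that applies is the one for related events. A site faced with such an event has two sets of instructions for one drug.

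Two things are at stake. Patients with the same event and grade can be held or not held, restarted at different doses, or stopped at different times. In addition, SAP 6.8 summarizes epacadostat dose reductions, mean daily dose and duration of treatment, and SAP 8.1 summarizes adverse events leading to discontinuation. Those figures would partly reflect the rule that was followed as well as the drug.

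**Working it through.** The plan states no figure to reproduce here, so the check sets the instructions side by side for the same event and grade.

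| Event | Table 6 | Table 8 / Section 5.4.3.2 |
|---|---|---|
| (a) Related Grade 2 diarrhea/colitis, AST/ALT/bilirubin, pneumonitis or renal event, resolved at 3 weeks | Hold; restart one level lower | Hold optional; same dose permitted |
| (b) The same event, unresolved at 8 weeks | Within the 12-week limit | Past the 6-week limit: discontinue or discuss with the Medical Monitor |
| (c) Grade 3 colitis, still above 10 mg/day prednisone at week 8 | Within the 12-week steroid limit | Past the 6-week steroid limit: discontinue |
| (d) Grade 3 pneumonitis or renal event | Permanently discontinue | Withholding also permitted; restart possible after discussion |
| (e) Grade 4 hypophysitis, hypothyroidism, or hyperglycemia with beta cell failure | Continue, or resume when stable | Section 5.4.3.2: all study drugs stopped permanently. Table 8: epacadostat stopped unless an exception is approved |

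**Reach of each row.**

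- (a) is limited to the named rows. For other Grade 2 drug-related events, Table 6 footnote 3 also makes the hold discretionary.
- (b) and (c): the limits differ by a factor of 12/6 = 2. The steroid thresholds also differ: exactly 10 mg/day meets Table 6 but not Table 8.
- (c) applies only where Table 6 does not already stop the drug for good at Grade 3: colitis, hyperthyroidism, hypophysitis and the all-other row. It does not apply to Grade 3 pneumonitis or renal events, nor to hepatic events outside their footnoted exception.
- (e) is confined to the endocrine and metabolic rows. At Grade 4, Table 6 agrees with Section 5.4.3.2 for colitis, hepatic events, hyperthyroidism, pneumonitis, renal events and all other toxicity. The hypophysitis row is also unclear internally: one cell lets epacadostat continue, and the next calls for a one-level reduction if related.
- Table 7 likewise lets pembrolizumab continue or resume in these endocrine and metabolic rows, but its own note requires permanent discontinuation for any life-threatening event.

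**Size of one dose level.** Section 5.4.2 refers to dose levels set out in Table 6, but Table 6 lists none, so the step has to be assumed.

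- If Table 3 (run-in level 1 to level -1) supplies it: 300 mg BID = 600 mg/day against 100 mg BID = 200 mg/day. The difference is (600 - 200)/600 = 67%.
- Table 11 has a 200 mg BID column, though nothing calls that a reduction level. If it were the step: 400 mg/day, and (600 - 400)/600 = 33%.

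The range for case (a) is therefore 33% to 67% of the daily dose, depending on a step that the protocol does not define.

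**The case against.** The strongest reply is that a site can often satisfy both sources at once. Table 8 is permissive at Grade 2, so holding and reducing under Table 6 breaches nothing in it. Stopping for Grade 3 pneumonitis satisfies both tables, and staying on hold past 6 weeks after a discussion satisfies both as well. This stands. A reader might infer that the tables give opposite orders, but the wording does not support that. In (a), (b) and (d), Table 8 allows a course that Table 6 does not, or adds an earlier decision point.

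Second, decisions are partly centralized. Section 5.4.3.3 wants irAEs of Grade 2 or higher discussed with the Sponsor at once. Section 5.4.1 requires discussion with the Medical Monitor before resuming after interruptions over 2 weeks or for liver-test abnormalities, and notice to the Medical Monitor before any restart after an adverse-event interruption. This also stands, and it reduces the practical effect. It does not tell the Medical Monitor which table to apply.

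Third, Table 8 is labelled as general guidance, and Section 5.4.2 presents Section 5.4.3.3 as additional information, so a specific-over-general reading is available. The protocol never states it, and Table 8 contains explicit withhold, restart and discontinue instructions. Similarly, the word *other* in the heading of Section 5.4.3.2 may exclude events already covered in Section 5.4.3.1. The sentence itself carries no such limit, and Table 8 at Grade 4 differs from the same Table 6 rows in any case.

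Finally, the Safety Review Committee makes the epacadostat dose decisions using DLTs and safety data, and the SAP 6.8 summaries are descriptive. A reader might infer that tolerability cannot be read from the data. That does not follow: DLTs, Grade 3 or higher events and adverse events of special interest are reported separately.

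**Conclusion.** The inconsistency is real and is confined to cases (a) to (e), plus the missing list of dose levels. The clearest conflicts are (c), where one source requires discontinuation at a point where the other does not, and (e), where the outcome for a Grade 4 endocrine or metabolic event depends on the section consulted. A reader might infer that Section 5.4.3.2 contradicts Table 6 for Grade 4 events in general; it does so only in those rows.

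The time limits differ twofold. The dose difference in (a) is 300 versus 100 mg BID only if the Table 3 step is assumed. The consequence for the SAP 6.8 summaries is partial confounding by the rule applied. The documents do not show how often such events occurred or which rule sites used, so the size of that confounding cannot be estimated. SAP 3.5 records that by 12 January 2018 all but 2 subjects had completed their end-of-treatment visit. Few patients could still be affected, but the reductions and discontinuations already recorded were made under these rules.

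**What to change.** The sponsor should do the following; which clinical rule stands is the sponsor's decision.

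- Reconcile Tables 6, 7 and 8 and Section 5.4.3.2, covering hold, restart level, time limit and steroid limit for each toxicity and grade. Alternatively, state which source governs when an event is both a toxicity listed in Table 6 and an irAE.
- State whether the Grade 4 sentence in Section 5.4.3.2 covers the hypophysitis, hypothyroidism and diabetes/hyperglycemia rows of Tables 6 and 7.
- List the dose levels to which a one-level epacadostat reduction refers.

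The cost is amendment text only, with no added procedures or patients. For data already collected, a sentence beside the SAP 6.8 summaries noting that reductions and discontinuations may have followed either table would be enough.
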